	3.4. Unanticipated serious adverse device effect (USADE)	
14.4.	Medical care of subjects	31
14.5.	Reporting and timelines	
14.5	5.1. Investigator's reporting responsibilities	
	Suspension or premature termination of the clinical investigation	
	Clinical investigation report	
	Publication policy	
18. B	Bibliography	35

LIST OF TABLES

Table 1 Chart showing scheduled visits and corresponding assessments,	22
Table 2 Anticipated adverse device effects	30
Table 3 Example illustrating test of adhesive strip -figure 1 and 2	14/15

> SYNOPSIS OF THE CLINICAL INVESTIGATION

Objectives

The primary objective is to investigate water absorption in different adhesives.

Secondary objectives are

- To investigate the impact that different water absorption properties in adhesives have on the initial adhesion, adherent area and skin when applied to skin exposed to buffer, output (simulated in part A and real/simulated output in part B of the study) as well as to dry skin.
- To investigate the impact that different water absorption properties in adhesives have on the adhesion during use with and without conducting exercise (part A and B).
- To explore the variations of adhesive properties when applied to peristomal skin and abdominal skin (part B)
- To explore the variations in water loss and hydration between peristomal skin and abdominal skin (part B)

Primary endpoint and secondary endpoint(s)

Primary endpoint:

1. Swelling of adhesive strips measured by weight (Difference between weight of strip before and after test)

Secondary endpoints:

- 2. Peel force needed to peel off adhesive strip (assessed when possible)
- Adherent area on adhesive strip assessed by photos and measured by area (cm²) or ordinal point scale ranging from very small to very large.
- 4. Trans Epidermal Water Loss (TEWL)
- 5. Hydration measured by conductance
- Redness of skin (erythema) assessed by spectrophotometric method and photos and potential video sequences
- 7. pH of skin
- 8. Discomfort when adhesive strip is peeled off and discomfort during use of adhesive strips

Pass/fail criteria

No formal success criteria are applied in this explorative investigation. The investigation will provide valuable insight into water absorption properties of different adhesives and to which degree these impact the adhesion and skin as well as insights to a potential resemblance between abdominal and peristomal skin.

Design of the investigation

The investigation is open-labelled and is divided into two parts: Part A evaluates the adhesive strips on abdominal skin in healthy volunteers while part B evaluates the adhesive strips on peristomal and abdominal skin in people with a stoma.

Population

Part A:

Inclusion criteria:

- 1. Have given written informed consent
- 2. Be at least 18 years of age and have full legal capacity
- 3. Have intact skin on the area used in the investigation

Exclusion criteria

- 1. Currently receiving or have within the past 2 months received radio- and/or chemotherapy
- 2. Currently receiving or have within the past months received topical steroid treatment in the abdominal skin area or systemic steroid (tablet/injection) treatment.
- 3. Are pregnant or breastfeeding
- 4. Have dermatological problems in the abdominal area (assessed by investigator)

Part B

Inclusion criteria:

- 1. Have given written informed consent
- 2. Be at least 18 years of age and have full legal capacity
- 3. Have had a stoma for more than one year
- 4. Has an ostomy with a diameter up to 35 mm
- 5. Have intact skin on the area used in the investigation

Exclusion criteria

- 1. Currently receiving or have within the past 2 months received radio- and/or chemotherapy
- 2. Currently receiving or have within the past month received topical steroid treatment in the peristomal skin area or systemic steroid (tablet/injection) treatment.
- 3. Are pregnant or breastfeeding
- 4. Have dermatological problems in the area used in the investigation (assessed by investigator)

Test products

The study includes a range of different adhesive strips with different water absorption properties.

Investigation approval

Adhesive strips are not considered medical devices and therefore, approval of the clinical investigation from the competent authorities is not deemed necessary.

> LIST OF ABBREVIATIONS

ABBREVIATION	DEFINITION	EXPLANATION (IF APPLICABLE)
ADE	Adverse Device Effect	See section 14.3.3
AE	Adverse Event	See section 14.3.3
ASADE	Anticipated Serious Adverse Device Effect	See section 14.3.3
CIP	Clinical Investigation Plan	
CRF	Case Report Form	Questionnaire to be used for data collection
СМ	Clinical Manager	
DQF	Data Query Forms	A DQF is specifically used in clinical research. The DQF is the primary data query tool used by the sponsor to clarify discrepancies and ask the investigator for an explanation. The DQF is part of the data validation process in a clinical investigation.
EC	Ethics Committee	

1.2 Investigators

PRINCIPAL INVESTIGATOR & MEDICAL ADVISOR	INVESTIGATOR REPRESENTATIVE

2. Identification and description of the investigational material

The study includes a range of different adhesive strips with different water absorption properties.

Adhesive strips are not considered medical devices and therefore, approval of the clinical investigation from the competent authorities is not deemed necessary.

3. Justification for conducting the clinical investigation

The adhesives in the ostomy baseplates are developed to make the ostomy product seal to the skin and thereby minimise the risk of leakage episodes.

The purpose of the study is to investigate and understand how different water absorption properties in adhesives affect the initial adhesion and the adhesion during use to human skin.

The data from the investigation will be used to optimize the water absorption properties in adhesives to be implemented in future ostomy products.

Furthermore, data from abdominal skin and peristomal skin are compared to explore the resemblance between the two skin types. This will provide valuable knowledge for the development of ostomy products/adhesives and may minimize the number of clinical studies in ostomy users in the early development phase.

4. Ethical considerations, investigational material and clinical investigation risks and benefits

The clinical investigation is conducted in accordance with current law and applicable standards see section 12.

The rights, safety and well-being of human subjects shall prevail over interest of science and society.

4.1. Anticipated benefits

There is no immediate benefit by participating in the study, however participating subjects will contribute with important information for developing new ostomy products that may reduce skin damage caused by leakage.

4.2. Anticipated risk, side effects and disadvantages

Part A of the study includes healthy volunteers and Coloplast employees. Previous, investigations have been conducted where the participants were Coloplast employees (e.g. journal No 2004-1-47G) and among especially development engineers, there is a wish to participate in the product development/adhesive development as they can obtain valuable knowledge on how it feels to apply, wear and remove adhesives and thereby use this knowledge to the development of the optimal adhesive for ostomy users. Furthermore, this investigation includes only objective endpoint measurements and therefore, it is considered acceptable to include employees. Employees are seen as a vulnerable group and therefore, recruitment and the informed consent procedure are focusing on voluntariness — and will comply with Helsinki declaration which describes that in such situations the informed consent must be sought by an appropriately qualified individual who is completely independent of this relationship.

There are no anticipated high risks during this clinical investigation. However, when performing the peel force of the skin the risk of mild to moderate skin irritation exists.

5. Objectives and hypotheses of the clinical investigation

5.1. Objectives

The primary objective is to investigate water absorption in different adhesives.

Secondary objectives are

- To investigate the impact that different water absorption properties in adhesives have on the initial adhesion, adherent area and skin when applied to skin exposed to buffer, output (simulated in part A and real/simulated output in part B of the study) as well as to dry skin.
- To investigate the impact that different water absorption properties in adhesives have on the adhesion during use with and without conducting exercise (part A and B).
- To explore the variations of adhesive properties when applied to peristomal skin and abdominal skin (part B)
- To explore the variations in water loss and hydration between peristomal skin and abdominal skin (part B)

5.2. Risks and anticipated adverse device effects to be assessed

There are no specific risks or anticipated adverse events to be assessed in this clinical investigation. However, when performing the peel force of the skin the risk of mild to moderate skin irritation exists.

6. Design of the clinical investigation

6.1. General

The investigation is open-labelled and is divided into two parts: Part A evaluates the adhesive strips on abdominal skin in healthy volunteers while part B evaluates the adhesive strips on peristomal and abdominal skin in people with a stoma.

Part A:

Investigation of adhesive strips will be performed in cohorts of minimum 4 and up to 80 subjects. Each cohort consist of 1 or more test visits and a compliance visit. The purpose of the investigation for the individual cohorts will be described in a sub-investigation document.

At each of the test visits, subjects have a maximum of six adhesive strips placed on the skin as illustrated in Figure 1. The adhesive strips are placed on either dry skin or skin wetted by buffer or simulated output. The adhesive strips can be removed at different time slots but after 72 hours at the latest (e.g. after 10, 60 minutes and 24 hours) or within the same time slot.

The ordering of the timeslots position (T1, T2 and T3) from belly - button will be randomized within each cohort if applicable.

Subjects can be asked to take a shower or ride an exercise bicycle for max 1 hour before application of adhesive strips or during wear.

Subjects can also be asked to apply and change adhesive strips every 24 hours between visits but for a maximum of 10 days between two visits. The strips should be applied at the same place every time

Each adhesive strip will be evaluated in a cohort of minimum 4 subjects and up to 80 subjects are enrolled and can test maximum 30 different types of adhesive strips.

Example illustrating test of adhesive strips. T1, T2 and T3 indicates different time slots for removing adhesive strips e.g. 10, 60 minutes and 24 hours:

[figure not shown]

Figure 1

Part B:

At each of the test visits, subjects have a maximum of four adhesive strips placed on the skin as illustrated in the Figure 2. The adhesive strips are placed on either dry skin or skin wetted by buffer, real or simulated output. The adhesive strips will be removed at different time slots but after 72 hours at the latest.

Subjects can be asked to take a shower or ride an exercise bicycle for max 1 hour before application of adhesive strips or during wear.

Subjects can also be asked to apply and change adhesive strips in the abdominal area every 24 hours between visits but for a maximum of 10 days between two visits. The strips should be applied at the same place every time.

Each adhesive strip will be evaluated in a cohort of minimum 4 subjects and up to 50 subjects are enrolled and can test maximum 30 different types of adhesive strips.

The ordering of the timeslots position (T1 and T2) from belly-button will be randomized within each cohort if applicable.

Example illustrating test of adhesive strip. T1 and T2 indicates different time slots for removing adhesive strips e.g. 1 and 24 hours:

[figure not shown]

Figure 2.

6.1.1. Primary end point

Primary endpoint:

1. Swelling of adhesive strips measured by weight (Difference between weight of strip before and after test)

6.1.2. Secondary end points

Secondary endpoints:

- 2. Peel force needed to peel off adhesive strip (assessed when possible)
- 3. Adherent area on adhesive strip assessed by photos and measured by area (cm²) or ordinal point scale ranging from very small to very large.
- 4. Trans Epidermal Water Loss (TEWL)
- 5. Hydration measured by conductance
- 6. Redness of skin (erythema) assessed by spectrophotometric method, thermography, photos and potential video sequences
- 7. pH of skin
- 8. Discomfort when adhesive strip is peeled off evaluated by the Visual Analogue Scale (VAS) and discomfort during use of adhesive strips evaluated by following questions: 1) Have you experienced any redness under the adhesive? 2) Have you experienced any itching or burning under the adhesive? 3) Do you experience any weeping or moisture on the skin under the adhesive? 4) Have you experienced any pain under the adhesive? 5) Do you experience any bleeding from the skin under the adhesive? The severity of redness, itching and burning, weeping and moisture, pain and bleeding will be rated as None of the time, A little of the time, Some of the time, A lot of the time or All of the time.
- 9. Adverse events

TEWL, hydration, occurrence of erythema and pH of the skin are measured by three repeated measurements.

Baseline data:

Age Gender Height/weight Informed Consent

For Part B the following will be included as well:

Year of stoma

Type of stoma

Reason for stoma

Leakage pattern

Experiences with moisture and product performance (e.g. skin maceration, leaks after physical activities etc.)

– Answer is a comment field

6.1.3. Rationale for the selection and measurement of end points

Peel force: Peel force is a very frequently used and relevant method for recording adhesive properties of new developed skin adhesives. It describes how good the adhesives stick to the skin. [2, 3]. Peel force is measured by peeling the adhesive strips from the skin surface

Adherent area: After peeling the adhesive strips from the skin surface a picture of the adhesives is taken. Based on visual inspection from the picture, the area not affected by water or output is considered the adherent area, which is a measurement for adhesives ability to resist moisture and output. The adherent area is measured by a ruler/ordinal 5-point scale.

Swelling of adhesives strips: The swelling of the adhesive strips measured by the difference in weight before and after test is an indicator of the ability of the amount of moist that the adhesive strips can absorb.

Trans Epidermal Water Loss (TEWL): TEWL is a standardized non-invasively method for describing the barrier function of the skin [1]. Damage to the skin surface (stratum corneum) will lower the barrier of the skin and thereby increase the water loss. This can be used as a proxy for the damaging effects of the adhesive.

TEWL is measured by applying a probe to the surface of the skin. The instrument is a Dermalab (Cortex Technology A/S, Hadsund).

Skin Conductance and Capacitance (hydration): Conductance and Capacitance is standardized non-invasively methods for measuring the hydration of the skin [1]. Both the conductance and capacitance is proportional to the skins hydration state and how the skin is influenced by adhesives. The capacitance measurement can measure deeper in the skin whereas the conductance measures in the top layer of the skin. Both measurements are done by applying a probe to the surface of the skin. The instruments is either a DermaLab (conductance, Cortex Technology A/S, Hadsund) or a MoistureMeterD (capacitance, Delphin Technology).

Occurrence of erythema: A change in the surface skin color is known to be related to a change in the blood flow. This can be measured non-invasively with a spectrophotometric instrument (Dermaspectrophotometer, Cortex Technology A/S, Hadsund) where both the redness and the color of the skin are measured.

pH: How the skin PH is influenced by adhesives. (applying a probe to the surface of the skin)

Discomfort: The VAS is an instrument used to subjectively evaluate the discomfort when the strip is peeled off. The subject will be asked to mark the evaluation as a vertical line on the 10 cm horizontal VAS ranging from "no discomfort" to "worst possible discomfort" caused when the strip is peeled off. Discomfort during use

of adhesive strips evaluated by questions regarding subject experience in redness under the adhesive, feeling of itching and burning under the adhesive, weeping or moisture under the adhesive, pain and bleeding from the skin.

User experience is a very important part of product development in Coloplast A/S and the selected questions relate to how the adhesive strips affects the skin.

Adverse Events: All adverse Events are captured and documented throughout the study.

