6.2.2. Activities performed by sponsor representatives

The investigation will be conducted at a clinical facility at Coloplast, [name]. The Principal Investigator is overall responsible for the investigation. The sponsor representatives will be present at all study activities and all subjects visits.

During the investigation, sponsor's representatives will monitor the investigation closely.

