6.2.6. Blinding

This investigation is not blinded.

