12.3. Data protection

Information about the subject's identity is filed as a confidential document by the investigator(s) and subjects are referred to only as numbers on all other documents. The data are blinded correspondingly in the data analysis.

Should the investigation require future review, EC will be allowed access to all relevant information for audit and inspection purposes.

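### Adherent area is read by eye from photographs with nothing to mask the reader; coded reading in mixed random order would cheaply reduce, though not remove, reader bias

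*Combined protocol and SAP*

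**What the plan says.** Section 6.1.2 lists the endpoint as "Adherent area on adhesive strip assessed by photos and measured by area (cm²) or ordinal point scale ranging from very small to very large". Section 6.1.3 explains the reading: a picture is taken after the strip is peeled off, and "Based on visual inspection from the picture, the area not affected by water or output is considered the adherent area". It adds that "The adherent area is measured by a ruler/ordinal 5-point scale". The same section treats the result as a measure of how well the adhesive resists moisture and output, and a secondary objective in 5.1 names adherent area.

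On masking, section 6.2.6 says "This investigation is not blinded" and makes no separate rule for photographs. The only other use of the term is in 12.3: "The data are blinded correspondingly in the data analysis". There it follows a sentence on referring to subjects by number, so it concerns subject identity, not adhesive identity.

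The flow chart (6.2.4) has the investigator apply the strips and take the photograph. It does not say who reads it. Section 6.2.2 places the study at the sponsor's own facility and says "The sponsor representatives will be present at all study activities and all subjects visits". Under 8.1 the sponsor also manages and analyses the data.

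**The concern.** The line between affected and unaffected adhesive is a judgement, whether it is then measured with a ruler or graded on five points. A reader who knows which formulation is on the strip, how long it was worn and whether the skin was wetted can be led by what they expect to see.

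If that expectation differs between adhesives, it adds a systematic shift to the difference between them. Enrolling more subjects narrows the interval around the shifted value but does not move it back.

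Cohort results are used as they arrive to guide which adhesives are developed and tested next (7.1, 7.5), so a distorted reading could influence that choice even though the study has no pass/fail criterion (7.4).

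Open conduct does not make this unavoidable. The reading is made on a stored picture after removal, so the reader can be masked without changing any visit, application or removal.

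**Working it through.** **What the protocol provides**

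| Question | Where | Answer |
|---|---|---|
| How is the boundary set? | 6.1.3 | By eye, on a photograph |
| On what scale? | 6.1.2, 6.1.3 | Area by ruler, or ordinal five-point grade |
| Is the study blinded? | 6.2.6 | No |
| Who reads the photograph? | 6.2.4 | Not stated; the investigator applies the strip and takes the photograph |
| Are photographs coded, or is there a masked or second reader? | 6.1.3, 6.2.1, 6.2.4, 6.2.6, 12.3 | Not provided for |
| Can the photograph be read later? | 6.1.3, 6.2.1 | Yes, it is taken after removal |

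The protocol gives no SD, effect size or power for adherent area, so it has no figure to reproduce.

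**Illustration of size**

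Inputs from the protocol: minimum cohort of 4 (7.1, 7.2); a 5% level if exploratory tests are done (7.3).

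Assumptions: two-sided test; no true difference; reader expectation shifts one adhesive relative to another by *b* SD, with *b* from 0 to 0.5. In the paired case the SD is that of the within-subject difference. In the two-group case it is the SD between subjects.

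The rejection rate is P(|T| > t₀.₉₇₅,df), where T is noncentral t with noncentrality δ:

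- paired: df = n − 1, δ = b√n
- two groups of n: df = 2n − 2, δ = b√(n/2)

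For n = 4:

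- Paired, critical value 3.182 on 3 df. b = 0.3: δ = 0.3 × 2 = 0.60, rejection 7.2%. b = 0.5: δ = 0.5 × 2 = 1.00, rejection 11.1%.
- Two groups, critical value 2.447 on 6 df. b = 0.3: δ = 0.3 × 1.414 = 0.42, rejection 6.5%. b = 0.5: δ = 0.5 × 1.414 = 0.71, rejection 9.2%.

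| Subjects per adhesive | b | Paired | Two groups |
|---|---|---|---|
| 4 | 0 | 5% | 5% |
| 4 | 0.2 | 6.0% | 5.7% |
| 4 | 0.3 | 7.2% | 6.5% |
| 4 | 0.5 | 11.1% | 9.2% |
| 20 | 0.3 | 24.7% | 15.2% |
| 20 | 0.5 | 56.5% | 33.8% |

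The rows for 20 subjects only show the direction of travel. The protocol allows cohorts of 4 to 80 in part A (6.1) but names no cohort of 20.

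**Workload**

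The ceiling on strips is 80 × 25 × 6 = 12,000 in part A and 50 × 25 × 4 = 5,000 in part B, 17,000 in all. This takes every permitted maximum at once and is not a planned number.

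**The case against.** The sponsor can fairly answer as follows.

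- **Coding cannot hide everything.** The feature being scored is how far water or output has affected the strip, so an output-exposed strip may be distinguishable from a dry one, and some formulations may look different. This stands: coding reduces the bias and does not remove it.
- **Coding within a cohort may achieve little.** If a cohort tests one adhesive, its reader knows the adhesive whatever the label says, and the joint evaluation in 7.1 rests mainly on cohort summaries. This stands, and it is why the photographs must be mixed across adhesives or cohorts.
- **The size is hypothetical.** The shift is assumed, the protocol specifies no paired analysis, a t test does not naturally suit the ordinal scale, and testing is optional because evaluation is primarily by summary statistics (7.3). This also stands. A reader might infer a false-positive rate of 25–57%, but that needs a shift of 0.3 to 0.5 SD, a paired test and 20 subjects, none of which the protocol states.
- **No direction of bias is shown.** The protocol names no favoured product. Section 6.2.2 shows that sponsor representatives attend visits, not that they read photographs. The documents therefore support a risk of bias, not evidence that it occurs or which way it runs.
- **The stakes are limited.** This is a secondary endpoint in an exploratory study. Peel force also measures adhesion, and laboratory data support the decisions (7.1, 7.2). This limits the importance of the point but is no reason to leave the reading unmasked.

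A reader might also take the statement in 4.2 that "this investigation includes only objective endpoint measurements" as a claim that photograph reading needs no masking. In context it justifies enrolling employees as subjects, and subjects do not score adherent area, so it bears little on this point.

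**Conclusion.** The point holds as a low-cost improvement to one secondary endpoint. Adherent area depends on visual judgement, the study is open, and no provision keeps the reader from knowing the adhesive, time slot or condition. Masked reading of a stored photograph is feasible and is better than the stated method.

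The size of the bias cannot be derived from the documents. Under an assumed shift of 0.3 to 0.5 SD, the false-positive rate at the minimum cohort size is modestly above the nominal 5%. The rate grows with cohort size, and the means and listings that the sponsor will mainly use carry the shift whether or not a test is run.

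Two stronger readings are not supported: that coding would eliminate reader bias, and that the study's main result is in doubt. The primary endpoint is a weight difference and does not depend on reading photographs.

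**What to change.** Amend 6.1.3 and 6.2.6 to state that:

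1. each strip photograph carries only a random code;
2. existing staff read the photographs after the visit, in random order and without the allocation list, where possible by someone who neither applied nor photographed that strip;
3. where a cohort tests only one adhesive, its photographs are mixed with those of other adhesives or cohorts, or are re-read in mixed coded order before the joint evaluation in 7.1;
4. codes are linked to adhesive, time slot and condition only after all readings in that batch are entered.

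The clinical report should acknowledge that some adhesives or wetting conditions may remain recognisable.

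The cost is labelling work and a short delay before cohort readings are available; a re-read adds reading time. No extra visit, strip or photograph is needed. The documents give neither costs nor a planned number of photographs, so the sponsor should judge the workload from its actual cohort plans.
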